8.4 Sample Size and Power Estimation

We computed the sample size needed to assess RZV effectiveness against HZ and PHN. We estimated that the incidence of HZ ranges from 10 to 15/1,000 person-years in the RZV unvaccinated group, and that the incidence of PHN ranges from 1.0 to 1.5/1,000 person-years in the RZV unvaccinated group, and the censoring rates in the RZV vaccinated and RZV unvaccinated groups are 7% and 15% per year, respectively. We expect a higher drop out over time in the RZV unvaccinated group due to receipt of RZV.

The sample size calculation was conducted using a two-sided log rank test with alpha=0.05, to achieve 80% statistical power, based on certain assumptions for incidence rate in the RZV unvaccinated group, follow-up period, censoring rate, matching ratio, and detectable HR (or VE). The calculation was performed using SAS software package (version 9.3) PROC POWER procedure.

Assumptions for sample size calculation:

- Incidence of HZ in the RZV unvaccinated group: 10, 12, 15/1,000 person-years
- Incidence of PHN in the RZV unvaccinated group: 1.0, 1.2, 1.5/1,000 person-years
- Follow-up period: 5 or 10 years after the second dose of RZV
- Censoring rate in the RZV vaccinated group: 7%
- Censoring rate in the RZV unvaccinated group: 15%
- Ratio of RZV unvaccinated to RZV vaccinated group: 4:1
- Detectable HR (or VE): 0.1, 0.2, 0.3, or 0.4 (VE=90%, 80%, 70%, or 60%)

Table 3 to Table 6 below present the sample size estimated to be sufficient to detect a HR of PHN and HZ between the vaccinated and unvaccinated cohorts with a follow-up period of 5 years (interim report) or 10 years (complete follow-up period). The study sample size is determined based on a conservative approach for subgroup analysis of VE against PHN. Given a PHN incidence of 1/1,000 person-years in the RZV unvaccinated group, application of censoring rates in the RZV vaccinated and RZV unvaccinated groups, and 5 years of follow-up, we need 5,836 patients with completion of two doses of RZV for a subgroup analysis to achieve 80% of power of detecting a HR of 0.4 (60% VE).

Assuming that Black race/ethnicity is a reasonably small subgroup (which contributes 6.5% of vaccinated patients), that 40% of patients who receive one dose of RZV will not complete their second dose between 4 weeks and 6 months of their first dose, and that 7% of patients will not meet the requirement of 1-year membership prior to index date, the proposed sample size receiving at least one dose of RZV during the vaccine accrual period will be 160,900 patients (=5836/0.065/0.6/0.93). The target sample size of the 2-dose RZV cohort meeting eligibility criteria and with their second dose between 4 weeks and 6 months of their first dose is 89,785 (=5836/0.065). Given 1.67 million current active members aged 50 years and older in KPSC, we estimate that 1.4 million unvaccinated members will be eligible for matching. It is feasible to match unvaccinated patients 4:1 to vaccinated patients in the 2-dose (4 weeks to 6 months) RZV cohort by age, *sex and race/ethnicity (Amended 17 February 2022)*.

Table 3. Sample size estimation for PHN with 5 years follow-up

Incidence rate in RZV unvaccinated group (cases/1,000 person- years)	HR	VE (%)	Total Sample Size	Sample size of RZV vaccinated group
	0.1	90	11,890	2,378
1.0	0.2	80	15,505	3,101
1.0	0.3	70	20,845	4,169
	0.4	60	29,180	5,836
	0.1	90	9,910	1,982
1.2	0.2	80	12,920	2,584
1.2	0.3	70	17,370	3,474
	0.4	60	24,320	4,864
	0.1	90	7,930	1,586
4.5	0.2	80	10,340	2,068
1.5	0.3	70	13,900	2,780
	0.4	60	19,460	3,892

Table 4. Sample size estimation for HZ with 5 years follow-up

Incidence rate in RZV unvaccinated group (cases/1,000 person- years)	HR	VE (%)	Total Sample Size	Sample size of RZV vaccinated group
10	0.1	90	1,190	238
	0.2	80	1,555	311
	0.3	70	2,095	419
	0.4	60	2,935	587
12	0.1	90	990	198
	0.2	80	1,295	259
	0.3	70	1,745	349
	0.4	60	2,450	490
15	0.1	90	795	159
	0.2	80	1,035	207
	0.3	70	1,400	280
	0.4	60	1,965	393

Kaiser Permanente **Research**

Table 5. Sample size estimation for PHN with 10 years follow-up

Incidence rate in RZV unvaccinated group (cases/1,000 person- years)	HR	VE (%)	Total Sample Size	Sample size of RZV vaccinated group
1.0	0.1	90	7,090	1,418
	0.2	80	9,300	1,860
	0.3	70	12,570	2,514
	0.4	60	17,685	3,537
	0.1	90	5,910	1,182
	0.2	80	7,750	1,550
1.2	0.3	70	10,475	2,095
	0.4	60	14,740	2,948
1.5	0.1	90	4,730	946
	0.2	80	6,200	1,240
	0.3	70	8,385	1,677
	0.4	60	11,800	2,360

Table 6. Sample size estimation for HZ with 10 years follow-up

Incidence rate in RZV unvaccinated group (cases/1,000 person- years)	HR	VE (%)	Total Sample Size	Sample size of RZV vaccinated group
	0.1	90	715	143
	0.2	80	940	188
10	0.3	70	1,275	255
	0.4	60	1,795	359
	0.1	90	595	119
10	0.2	80	785	157
12	0.3	70	1,065	213
	0.4	60	1,505	301
15	0.1	90	475	95
	0.2	80	630	126
	0.3	70	855	171
	0.4	60	1,210	242

8.5 Projected Study Timelines

In order to accrue a sufficient number of vaccinated individuals to power our primary analyses and certain secondary analyses covering a 5-year and 10-year follow-up period, we estimate that we will need 160,900 eligible individuals receiving at least one dose of RZV, or 89,785 eligible 2-dose (4 weeks to 6 months) RZV recipients with their second dose between 4 weeks and 6 months after their first dose. We will stop accrual when we reach our target sample size. Beginning with retrospective data from the first dose of RZV administered in April 2018, we expect to accrue the number of individuals receiving at least one dose of RZV administered in April 2018, we expect to accrue the number of individuals receiving at least one dose. The sample size is based on assumptions made for numerous factors noted in Section 0, including incidence rates of HZ and PHN, censoring rates, matching ratio, VE, 2-dose completion rate, and membership requirements. The following timeline (Table 7) is based on vaccine accrual and on the assumption that KPSC will not experience any interruption in RZV supply.

We estimate 50,000 persons per year will receive at least one dose of RZV (40,000 based on initial annual ZVL uptake plus an additional 10,000 annually due to eligibility of individuals aged 50-59 years to receive RZV). The total duration of the study activities will be approximately 16 years contingent upon assumptions and RZV supply. It is therefore feasible to accrue 160,900 eligible individuals receiving at least one dose of RZV and 89,785 eligible 2-dose (4 weeks to 6 months) RZV recipients over approximately 3-4 years and to have sufficient RZV unvaccinated individuals for the matched design.

Table 7. Study timelines and milestones (Amended 17 February 2022)

STUDY PHASE	ESTIMATED DATES	DESCRIPTION	
FIXED TIMELINES			
Estimated accrual period	April 2018 – Dec 2020	2.7 years of accrual	
RZV follow-up period	Jan 2021 – Dec 2030	10 years following administration of last completed 2- dose vaccination series	
Data settling	Jan 2031 – March 2031	~3 months after follow-up period to allow data settling for long hospitalizations and claims	
MILESTONES (DELIVERY DATE TO GSK)			
Final report (10-year follow-up)	October 2032		

We plan to submit brief annual progress report tables describing vaccine uptake during the estimated accrual period. After the accrual period is complete, we will provide more substantive annual reports including descriptive outcome information. We propose to report on the formal analyses of the objectives in the final report (10-year follow-up).

9. DATA MANAGEMENT AND DATA QUALITY

Data management activities will be performed by KPSC. The KPSC EHR will be the data source for extracting information on exposures, outcomes, and covariates. KPSC will develop the study datasets, maintain documentation, and perform data quality checks.

Programmers will extract data per protocol and reference documentation for KPSC EHR databases. They will conduct data quality checks which includes data integrity control, double programming, and program review. Data integrity control will include checks such as sample size, duplications, formatting, etc. Double programming (i.e., programming independently conducted by 2 people) will be performed on the cohort extraction as well as key outcome variables. The results of the original and validation programming will be compared, discrepancies will be investigated, and action will be taken to resolve discrepancies. Program review (i.e. a second person reviews the code of the lead programmer) will be performed on all programs that are not double-programmed. All decisions made during data extraction and data quality checks will be documented in a programming decision log.

Kaiser Permanente **Research**

10. ETHICAL AND LEGAL REQUIREMENTS

Federal Policy for the Protection of Human Subjects is codified by the Department of Health and Human Services 45 Code of Federal Regulations Part 46 which outlines the basic regulations governing the protection of human subjects in research, including requirements for assuring compliance by research institutions, requirements for obtaining and documenting informed consent, and requirements for Institutional Review Board (IRB) membership, function, operations, review of research, and record keeping.

The Health Insurance Portability and Accountability Act (HIPAA) Privacy Rule governs the use and disclosure of protected health information (PHI) from covered entities. Throughout the course of the study, no human subjects will be contacted or enrolled, and no PHI will be disclosed; however, PHI will be accessed through the EHR. This information will only be accessed by those authorized to do so and will not be shared with GSK or anyone outside of the KPSC study team. The KPSC team will obtain institutional approval to use PHI for research activities. Since this access to PHI presents no more than minimal risk to individuals, and the research could not be practically done if required to obtain written authorization for usage, we will obtain a waiver for written HIPAA authorization for research involving use of the EHR to conduct the study.

Additionally, all investigators and project managers are trained in the protection of human research participants, Good Pharmacoepidemiology Practices, and HIPAA. The KPSC Department of Research and Evaluation has policies in place to govern the conduct and administration of research at KPSC. These policies support compliance with federal and state regulatory requirements. Policies include conflict of interest, misconduct, sensitive data, and system access control. Policies are in place to ensure compliance with the Sunshine Act. All KPSC staff undergo annual compliance training and certification. The Principles of Responsibility is KPSC's code of conduct that addresses such issues as protection of confidential information and anti-bribery and corruption.

Kaiser Permanente **Research**

11. LIMITATIONS

A potential limitation of this study is that there could be differences between vaccinated and unvaccinated individuals that are difficult to control and measure. We will adjust for differences in demographic characteristics, health care utilization, and comorbidities, but differences in other unmeasured factors could result in residual confounding.

During the initial months of the vaccine accrual period, RZV vaccine at KPSC was prioritized for individuals ages 60 years and older. However, this should not bias results since individuals are matched on age.

Despite high validity of diagnostic algorithms, misclassification of HZ status could occur inherently in EHR studies using automated data, but this would only be a concern if misclassification was differential between exposure groups.

It is unknown if HZ vaccination leads to modified or atypical HZ presentations that are more likely to be underdiagnosed or misdiagnosed. If these cases are never diagnosed or are diagnosed as other conditions, they will not be identified through ICD-10 codes for HZ. This would lead to a potential overestimation of VE. This is less of a concern in this study, however, since the outcome of interest is defined to be medically-attended HZ diagnoses. It is also possible that there is differential misclassification of HZ due to differential health care seeking behaviors, but to address this, prior health care utilization is included as a covariate.

Kaiser Permanente **Research**

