Recombinant zoster vaccine (SHINGRIX, RZV), a two-dose subunit zoster vaccine containing recombinant glycoprotein E in combination with a novel adjuvant (AS01_B), was licensed by the FDA in 2017. This decision was based on two large parallel Phase III randomized controlled trials (RCTs): the Zoster Efficacy Study in Adults 50 Years of Age or Older (ZOE-50) and the Zoster Efficacy Study in Adults 70 Years of Age or Older (ZOE-70). ZOE-50 assessed whether RZV reduced the risk of HZ in adults 50 years of age or older. During a mean follow-up of 3.2 years, HZ was confirmed in 6 out of 7,698 participants in the vaccine group and in 210 out of 7,713 participants in the placebo group (incidence rate 0.3 vs. 9.1 per 1,000 person-years). Overall vaccine efficacy against HZ was 97.2% and ranged between 96.6% and 97.9% for all age groups evaluated [15]. In ZOE-70, the overall vaccine efficacy against HZ was 89.8% (6,541 vaccinated participants and 6,622 placebo participants) and was similar in participants 70-79 years of age (90.0%) and participants 80 years of age and older (89.1%) [16]. Although these Phase III RCTs were not powered to show statistical significance in serious adverse events, there were no observed differences between subjects vaccinated with RZV and comparison populations for the overall reported rates of serious adverse events [15]. Per indication, RZV is not contraindicated in persons with immunosuppressive conditions or treatments. Subsequent to FDA approval, ACIP made three recommendations: (1) RZV is recommended for immunocompetent adults aged 50 years and older; (2) RZV is recommended for immunocompetent adults previously vaccinated with ZVL; and (3) RZV is the preferred vaccine over ZVL [9].

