6.2 Outcome Definitions

6.2.1 Identification of HZ

HZ will be defined by International Classification of Diseases (ICD)-10 codes (B02.xx) from hospital, outpatient, and Emergency Department settings with an antiviral prescription (acyclovir, valacyclovir, famciclovir) within 7 days before or after the date of HZ diagnosis. Inclusion of an antiviral prescription as part of the HZ definition ensures identification of new HZ diagnoses, rather than carry-over codes from prior HZ episodes.

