8.3 Exploratory Analyses

Exploratory objective 1: We will estimate the VE of RZV in preventing HZ and PHN in adults aged \geq 50 years who completed 2 doses of the vaccine, but the second dose was received more than 6 months after the first dose (2-dose (>6 months) RZV cohort). The date of the second RZV dose will be the index date. We will use a similar analysis approach as was described for the primary objectives in Section 0.

Exploratory objective 2: We will assess VE of 2 doses of RZV (among the 2-dose (4 weeks to 6 months) RZV cohort) with concomitant vaccination (*e.g.*, receipt of influenza vaccine, pneumococcal vaccine, or Tdap) at the time of receiving either the first or second dose of RZV in preventing HZ in adults aged \geq 50 years. We will compare HZ incidence in individuals who received 2 doses of RZV and received another vaccine on the same day as either the first or second dose of RZV with RZV unvaccinated individuals. We will also compare the HZ incidence in individuals who received 2 doses of RZV and did not receive another vaccine on the same day as both the first and second dose of RZV with RZV unvaccinated individuals. For each of these analyses, we will estimate adjusted HRs and 95% CIs, and VE using methods similar to those described in Section 0.

Exploratory objective 3: We will conduct chart reviews to assess clinical characteristics related to the initial acute HZ episode for a sample of cases (100 2-dose (4 weeks to 6 months) RZV vaccinated HZ cases and 100 unvaccinated HZ cases). We will abstract clinical characteristics on the HZ episode from medical encounters 30 days before and after the initial HZ diagnosis, including: date of rash onset, date of HZ diagnosis, number of days from onset of rash to HZ diagnosis, affected dermatomes, location of rash, rash characteristics, severity of HZ, complications related to acute HZ, whether there was a positive test result for VZV (if available), specialty of provider making diagnosis, and antiviral prescription information. Clinical characteristics for vaccinated and unvaccinated cases will be presented as absolute numbers and percentages with p-values for the χ^2 test (categorical variables) or mean with standard deviation and/or median with interquartile ranges, with p-values for the two-sample t-test or Wilcoxon rank-sum test (continuous variables).

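### Section 11 dismisses non-differential HZ misclassification, but an equal false-positive rate in both arms lowers VE; the loss is unquantified and could exceed the confidence interval half-width

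*Supplement*

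**What the plan says.** Section 6.2.1 defines HZ by a B02.xx code together with an antiviral prescription within 7 days either side of the diagnosis. No chart or laboratory confirmation is required. The stated purpose of the prescription is to separate new episodes from carried-over codes: "Inclusion of an antiviral prescription as part of the HZ definition ensures identification of new HZ diagnoses".

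Section 11 describes the validity of the algorithms as high, without a figure, and then states that "misclassification of HZ status could occur inherently in EHR studies using automated data, but this would only be a concern if misclassification was differential". The rest of that discussion covers underdiagnosis of atypical HZ in vaccinees and differences in care seeking. It does not discuss false positives.

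Section 8.1 estimates HZ VE from an adjusted Cox model on these coded cases. Exploratory objective 3 (Section 8.3) is the only chart review of acute HZ episodes in general: "We will conduct chart reviews to assess clinical characteristics related to the initial acute HZ episode for a sample of cases", namely 100 two-dose vaccinated and 100 unvaccinated cases. It collects rash features, dermatomes and any VZV test result, and uses them only to describe and compare the two groups.

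**The concern.** The Section 11 sentence treats all non-differential misclassification alike. False positives add roughly the same absolute amount to each arm's rate. When the vaccine removes most true HZ, that amount is small beside the unvaccinated rate but large beside the vaccinated rate, so the rate ratio moves toward 1.

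The study asks whether the trial results hold in practice. Section 2 quotes trial efficacy of 97.2% (age 50 and over) and 89.8% (age 70 and over), and describes the cases in the first of these trials as confirmed. A shortfall caused by coding could be read as lower real-world effectiveness. Because the cohort is large, the published interval would be too narrow to warn the reader.

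**Working it through.** **Reproducing the plan's own figures.** The documents give no figure for misclassification bias, so the check is on the design inputs used below. A Lakatos log-rank calculation (4:1, two-sided 0.05, 80% power, censoring of 7% and 15% per year) gives totals of 29,004 or 29,259, depending on how the censoring rates are converted to hazards, for PHN at 5 years with HR 0.4; Table 3 states 29,180. For HZ at 5 years with HR 0.1 it gives 1,187 or 1,196; Table 4 states 1,190. The cohort target is 5,836/0.065 = 89,785 vaccinated, as stated.

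**Inputs.** Section 8.4: "Incidence of HZ in the RZV unvaccinated group: 10, 12, 15/1,000 person-years". True VE: 89.8% and 97.2% (Section 2), and 90% (the largest VE in Section 8.4). PPV in the unvaccinated arm: not given, so assumed to be 90% to 99%.

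**Equal sensitivity s.** The ratio is s·I0(1 − VE)/(s·I0) = 1 − VE. At s of 70%, 80% or 90%, a true VE of 90% still reads 90.0%. Here the protocol's statement is correct.

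**Equal false-positive rate f per person-year.**

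VE_obs = 1 − [I0(1 − VE) + f]/(I0 + f) = VE × I0/(I0 + f) = VE × PPV_u

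Example with I0 = 10 per 1,000 and PPV_u = 95%: f = 10 × 0.05/0.95 = 0.526.
- True VE 97.2%: vaccinated rate 0.280 + 0.526 = 0.806; 0.806/10.526 = 0.0766; VE reads 92.3%. PPV in the vaccinated arm is 0.280/0.806 = 35%.
- True VE 89.8%: vaccinated rate 1.020 + 0.526 = 1.546; 1.546/10.526 = 0.1469; VE reads 85.3%. PPV in the vaccinated arm is 1.020/1.546 = 66%.

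| Assumed PPV_u | True 89.8% reads | True 90% reads | True 97.2% reads | Loss (points) |
|---|---|---|---|---|
| 99% | 88.9% | 89.1% | 96.2% | 0.9–1.0 |
| 98% | 88.0% | 88.2% | 95.3% | 1.8–1.9 |
| 97% | 87.1% | 87.3% | 94.3% | 2.7–2.9 |
| 95% | 85.3% | 85.5% | 92.3% | 4.5–4.9 |
| 90% | 80.8% | 81.0% | 87.5% | 9.0–9.7 |

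For a given PPV_u the result does not depend on I0. For a given f it does: f = 0.5 per 1,000 turns 90% into 85.7% at I0 = 10 and 87.1% at I0 = 15, and turns 97.2% into 92.6% and 94.1%.

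**Random error for comparison.** Five-year person-years:
- Vaccinated: 89,785 × (1 − e^(−0.35))/0.07 = 378,780
- Unvaccinated: 359,140 × (1 − e^(−0.75))/0.15 = 1,263,295, which gives 12,633 cases at 10 per 1,000

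True VE of 90% gives 379 vaccinated cases, and 97.2% gives 106. With SE(log HR) ≈ √(1/d_v + 1/d_u), the 95% CIs are 88.9% to 91.0% and 96.6% to 97.7%. At 10 years they are 89.2% to 90.8% and 96.8% to 97.6%. These are crude approximations that ignore covariates.

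**The case against.** **The size is not established.** A reader might infer that VE will be understated by several points. The documents do not support that. They give no PPV, and a loss of about 3 points or more needs a PPV of 97% or lower in the unvaccinated arm. At 98% to 99% the loss is 1 to 2 points. The antiviral rule and the exclusion of people with HZ in the 6 months before index or within 30 days after it (Section 7.1) both favour the low end. Likewise, false positives become the majority of vaccinated cases only if PPV_u is below 1/(2 − VE), which is 97.3% at true VE 97.2% and 90.7% at 89.8%. This stands as a limit on the claim. It does not make the Section 11 sentence correct.

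**A correction may exist.** A reader might also infer that none is planned. The protocol describes none, but it refers to a SAP that is not shown, so nothing can be said about that document.

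**Strata.** The suggestion that false positives seriously distort comparisons between age groups is not supported. At PPV_u 95%, strata with true VE of 97.2% and 89.8% lose 4.9 and 4.5 points. The gap changes by about 0.4 points against a real difference of 7.4, unless PPV itself differs by stratum.

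**Equal PPV gives no bias.** True, but equal PPV would require vaccination to cut false-positive coding as much as true HZ. That is differential specificity, not the case Section 11 dismisses.

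**The bias is conservative.** It cannot create false protection and does not threaten power. PHN, the second primary outcome, is identified by chart review. This limits the seriousness, but the primary objective is to estimate VE, so a downward bias still matters.

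**Conclusion.** The sentence in Section 11 is wrong as a general statement, whatever the SAP contains. Equal sensitivity error is harmless to the ratio. An equal false-positive rate per person-year multiplies VE by the unvaccinated-arm PPV. For true VE of 90% to 97% the loss is about 1 point at PPV 99%, rising to 9 to 10 points at 90%. The approximate CI half-width at 5 years is about 1 point at VE 90% and about half a point at VE 97.2%, so even a 2-point loss would exceed it.

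The algebra depends only on the false-positive rate being equal in both arms. The size depends on an assumed PPV that the protocol neither gives nor plans to estimate. The point concerns the accuracy and interpretation of the HZ estimate, not the validity of a finding of protection.

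**What to change.** 1. Reword Section 11 to say that non-differential false positives lower VE, while equal imperfect sensitivity leaves the ratio unchanged.
2. In exploratory objective 3, draw the 100 + 100 charts at random from each arm's HZ cases. Classify each as confirmed or not confirmed HZ against a written definition built on the items already abstracted, and estimate PPV by arm. VZV results are recorded only where available, so the definition must also work without one.
3. Prespecify a sensitivity analysis beside the primary result: corrected VE = 1 − adjusted HR × (PPV_v/PPV_u), with a CI that carries the PPV sampling error. Using the adjusted HR rather than crude rates keeps it comparable with the primary Cox estimate. Also show VE over a stated PPV range.
4. State that this addresses false positives only. Missed atypical HZ in vaccinees, which Section 11 already notes, biases VE upward and is not corrected.

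The cost is a case definition and one added field on charts already planned, with a wider CI for the corrected VE. The widening is tolerable. With SE of log(PPV_v/PPV_u) = √[(1 − PPV_v)/(100·PPV_v) + (1 − PPV_u)/(100·PPV_u)] and PPV_u = 95%, PPV sampling error alone gives 96.3% to 97.9% around a true 97.2%, and 88.2% to 91.2% around a true 89.8%.
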